#### **6.2.6. Full 24 Month Analyses**

In general, the same analysis approach for the changes from baseline GA lesion size for the final reporting of the full 24 months will be repeated as described in Sections 6.2.2, 6.2.3, 6.2.4, 6.2.5. Key differences include:

- The definition of excessive missed/not received injection in the supplementary estimand will be defined based on the Month 24 period. The threshold for missed/not received injections due to the COVID-19 pandemic is missing 4 or more injections for the Monthly schedule group and 2 or more injections for the EOM schedule group prior to the Month 24 visit attributable due to the COVID-19 pandemic.
- The Month 12 PP set will be replaced with the Month 24 PP set for the supplementary analysis.

#### **6.2.7. Exploratory Endpoints Closely Related to the Primary Efficacy Endpoint**

Analyses of the following endpoints closely related to the primary efficacy endpoint, will be performed for the mITT set to provide supplemental information.

##### **6.2.7.1. Change in Square Root of GA Area**

For each subject and timepoint, the square root of GA area will be calculated. The change from baseline in square root of GA area will be analyzed using the same methodology as described for the primary endpoint analysis in Section 6.2.2, except that change from baseline in the square

root of GA area will be the response variable. This analysis will be conducted both for the first 12 months summaries as well as the full 24 months summaries.

### **6.2.7.2. Percent Change in GA Area and Square Root of GA Area**

For each subject and timepoint, the percent change in GA area will be defined as the change from baseline in GA area ( $\text{mm}^2$ ) divided by the GA area ( $\text{mm}^2$ ) at baseline and the percent change in square root of GA area will be defined as the change from baseline in GA area (mm) divided by the GA area (mm) at baseline. The percent change in GA area from baseline and percent change in square root of GA area will be analyzed using the same methodology as described for the primary endpoint analysis in Section 6.2.2, except that percent change from baseline will be the response variable. This analysis will be conducted both for the first 12 months summaries as well as the full 24 months summaries.

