6.1.1. Inclusion Criteria

The study eye must meet all inclusion criteria. If both eyes meet the inclusion criteria, the eye with the worst normal luminance visual acuity at the screening visit will be designated as the study eye. If both eyes have the same visual acuity, the right eye will be selected as the study eye.

Ocular-specific inclusion criteria apply to the **study eye** only, unless otherwise specified.

- 1. Age \geq 60 years.
- 2. Normal Luminance best corrected visual acuity of 24 letters or better using Early Treatment Diabetic Retinopathy Study (ETDRS) charts (approximately 20/320 Snellen equivalent).
- 3. Clinical diagnosis of GA of the macula secondary to AMD as determined by the investigator and confirmed by the reading center.
- 4. The GA lesion must meet the following criteria as determined by the central reading center's assessment of FAF imaging at screening:
 - a. Total GA area must be ≥ 2.5 and ≤ 17.5 mm2 (1 and 7 disk areas [DA] respectively).
 - b. If GA is multifocal, at least 1 focal lesion must be \geq 1.25 mm2 (0.5 DA), with the overall aggregate area of GA as specified above in 4a.
 - c. The entire GA lesion must be completely visualized on the macula centered image and must be able to be imaged in its entirety and not contiguous with any areas of peripapillary atrophy.
 - d. Presence of any pattern of hyperautofluorescence in the junctional zone of GA. Absence of hyperautofluorescence (ie, pattern = none) is exclusionary.¹
- 5. Adequate clarity of ocular media, adequate pupillary dilation, and fixation to permit the collection of good quality images as determined by the investigator.
- 6. Meets the following criteria related to microperimetry:
 - a. Able to detect fixation target.
 - b. Total elapsed time to complete the 10-2 68-point exam is ≤ 30 minutes in duration.
 - c. Fixation losses must be $\leq 20\%$.
 - d. Subject is willing and able to undertake microperimetry assessment in the opinion of the investigator.
- 7. Female subjects must be:
 - a. Women of non-childbearing potential (WONCBP), or
 - b. Women of childbearing potential (WOCBP) with a negative serum pregnancy test at screening and must agree to use protocol defined methods of contraception for the duration of the study and refrain from breastfeeding for the duration of the study.

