12.5. Sample Size Calculation and Power Considerations

Subjects will be randomized in a 2:2:1:1 ratio to receive treatment with pegcetacoplan monthly, pegcetacoplan every other month, sham monthly, or sham every other month. The annual growth rate in GA lesion area is expected to have a mean of 1.47, 1.70 and 2.13 mm²/year for pegcetacoplan monthly, pegcetacoplan every-other-month, and sham-pooled groups, respectively, as estimated from the results of a Phase 2 trial for pegcetacoplan. The standard deviation of the lesion growth is estimated to be 1.50 mm² based on the same Phase 2 trial data or 1.25 mm² based on natural history data.²¹ The following table provides an approximation of the study power for a sample size of 200 subjects in each group (ie, a total enrollment of 600 subjects) under different alpha values and standard deviations. The approximation is calculated using PROC POWER one-way analysis of variance, SAS 9.4. The study power is likely larger when utilizing the longitudinal data to model the primary endpoint. The actual study power may also vary based on the distribution of the stratification factors (ie, lesion area at screening, presence of CNV in fellow eye), and site enrollment.

Table 4: Power to Detect a Difference Among 3 Groups With an Equal Size of 200 Subjects

Common standard deviation (mm²)		Power for a true mean of 1.47, 1.70, and 2.13 mm ² /ye PM, PEOM, and sham, respectively							
	Alpha (2-sided)	PM vs sham	PEOM vs sham	Overall (among 3 groups)					
1.25	0.0495	> 99.9%	92.9%	99.9%					
1.25	0.0248	99.9%	88.2%	99.7%					
1.40	0.0495	99.7%	86.5%	99.3%					
1.40	0.0248	99.3%	79.4%	98.6%					
1.50	0.0495	99.2%	81.5%	98.4%					
1.50	0.0248	98.4%	73.1%	97.0%					

Abbreviations: PM = pegcetacoplan monthly; PEOM = pegcetacoplan every other month.

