#### **2.2.6. Exploratory Endpoints Closely Related to the Primary Efficacy Endpoint**

- Change from baseline in square root of the total area of GA lesion(s) in the study eye (in mm) based on FAF over time.
- Percent change in total area of GA lesion(s) in the study eye (in mm^2) based on FAF over time.
- Percent change in square root of the total area of GA lesion(s) in the study eye (in mm) based on FAF over time.

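### SAP 6.2.7.2 leaves the square root out of its formula for percent change in square root of GA area, an exploratory endpoint

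*SAP*

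**What the plan says.** SAP 2.2.6 lists percent change in total GA area and, as a separate endpoint, "Percent change in square root of the total area of GA lesion(s) in the study eye (in mm) based on FAF over time". SAP 6.2.7.1 prepares the variable needed for the second: "For each subject and timepoint, the square root of GA area will be calculated".

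SAP 6.2.7.2 then defines both percent changes in one sentence. The first is change in area over baseline area, labelled mm². The second is given as "square root of GA area will be defined as the change from baseline in GA area (mm) divided by the GA area (mm) at baseline". Both are sent through the repeated-measures model of SAP 6.2.2, which reports least-squares means, 95% confidence intervals and p-values. On timing, the section says: "This analysis will be conducted both for the first 12 months summaries as well as the full 24 months summaries".

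No other place supplies the formula. SAP 13.5.1 (GA lesion size) does not define the variable, the sample SAS code does not derive it, and the protocol's list of exploratory endpoints does not include it.

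**The concern.** The two formulas in SAP 6.2.7.2 name the same quantities. They differ only in the unit label, and because each is a ratio, the label does not change the number computed. A programmer working from the words alone would produce percent change in area twice, the second time under the wrong name, and the endpoint listed in SAP 2.2.6 would not be computed.

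The values at stake are the arm means and pegcetacoplan-sham differences reported for this one exploratory endpoint at 12 and 24 months. This is the plan's only operational definition of the variable, so the wording should be right.

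**Working it through.** The plan states no numerical result for this endpoint, so there is no figure to reproduce. The check compares the worded formula with the intended one.

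**Inputs**
- Baseline area A0: the eligibility range in Protocol 6.1.1, "Total GA area must be ≥ 2.5 and ≤ 17.5 mm2", with 7.5 mm² (the stratification cut-point) as a middle value.
- Growth: Protocol 12.5, repeated in SAP 3.4: "The annual growth rate in GA lesion area is expected to have a mean of 1.47, 1.70 and 2.13 mm²/year", for PM, every-other-month pegcetacoplan (PEOM) and pooled sham respectively.
- Area at the visit: A1 = A0 + growth. For Month 24 the yearly growth is doubled; constant growth is an assumption.

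**Formulas**
- As worded: (A1 − A0)/A0.
- As intended: (√A1 − √A0)/√A0 = √(A1/A0) − 1.
- Worded over intended: since A1 − A0 = (√A1 − √A0)(√A1 + √A0), the ratio is (√A1 + √A0)/√A0 = 1 + √(A1/A0). This exceeds 2 for any lesion that has grown.

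**Example, A0 = 7.5 mm², Month 12**
- Sham: 2.13/7.5 = 28.4%; √(9.63/7.5) − 1 = 13.3%.
- PM: 1.47/7.5 = 19.6%; √(8.97/7.5) − 1 = 9.4%.
- Sham minus PM: 28.4 − 19.6 = 8.8 points as worded; 13.31 − 9.36 = 3.95, or 4.0 points, as intended.

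**Across the eligible range**

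| Month | A0 (mm²) | Arm | As worded | As intended | Factor |
|---|---|---|---|---|---|
| 12 | 2.5 | PM | 58.8% | 26.0% | 2.26 |
| 12 | 2.5 | Sham | 85.2% | 36.1% | 2.36 |
| 12 | 7.5 | PM | 19.6% | 9.4% | 2.09 |
| 12 | 7.5 | Sham | 28.4% | 13.3% | 2.13 |
| 12 | 17.5 | PM | 8.4% | 4.1% | 2.04 |
| 12 | 17.5 | Sham | 12.2% | 5.9% | 2.06 |
| 24 | 2.5 | PM | 117.6% | 47.5% | 2.48 |
| 24 | 2.5 | Sham | 170.4% | 64.4% | 2.64 |
| 24 | 7.5 | PM | 39.2% | 18.0% | 2.18 |
| 24 | 7.5 | Sham | 56.8% | 25.2% | 2.25 |
| 24 | 17.5 | PM | 16.8% | 8.1% | 2.08 |
| 24 | 17.5 | Sham | 24.3% | 11.5% | 2.12 |

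PEOM lies between PM and sham throughout. Individual lesions can fall outside these ranges. For example, growth of 3.63 mm² in a year (the sham mean plus one planning SD of 1.5) from 2.5 mm² gives 1 + √(6.13/2.5) = 2.57.

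**The case against.** The strongest reply is that the text does not tell the analyst to repeat percent change in area. Within one sentence the area formula carries mm² and the second formula carries mm, and an area cannot be measured in mm. The section heading and the term being defined both say square root. The next sentence treats the two percent changes as separate responses. SAP 2.2.6 and 6.2.7.1 both name the square root explicitly, and SAP 5.2 lists square-root lesion size in mm as a baseline characteristic. Read by its unit, the formula is the intended one and the factor is 1. A careful programmer would probably compute the right quantity.

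That reply stands as far as it goes. A reader might infer that the reported results will be more than doubled; the documents do not support this, because the inflation follows only if all these signals are ignored. A reader might also infer that the slip costs the area analysis an independent confirmation. It does not: for each subject the intended measure is √(1 + percent change in area) − 1, a one-to-one function of percent change in area, so even the correct formula adds no independent evidence.

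The reply does not make the definition correct. The words still name the wrong quantity in both terms, and the analyst must override them to obtain the listed endpoint.

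**Conclusion.** The definition is wrong as written, and the matter is minor. The operative sentence omits the square root from both terms and contradicts the endpoint it is meant to implement.

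The size is conditional on a literal reading. In that case the overstatement is 1 + √(A1/A0): 2.04 to 2.36 at Month 12 and 2.08 to 2.64 at Month 24. These ranges use planned mean growth applied to single baseline values between the eligibility limits, and the Month 24 range also assumes constant yearly growth. They illustrate the scale and do not predict model estimates.

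The endpoint is exploratory and lies outside the hypothesis-testing scheme of SAP 6.2.1 and 6.3.1. No primary or key secondary test, alpha level or sample size changes.

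**What to change.** In SAP 6.2.7.2, insert the words *square root of* before *GA area* in both the numerator and the denominator of the second definition and keep the mm unit. The formula then reads (√A1 − √A0)/√A0. Leave the area formula as it is.

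Neither formula currently shows a multiplication by 100. If one is added, add it to both, so that the two percent changes are on the same scale.

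The cost is one sentence in the SAP, with no new data and no additional analysis. If programs already exist, confirm that the derived variable uses the square root.

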## **6.3. Analyses of Key Secondary Efficacy Endpoints**

The key secondary efficacy endpoints are listed in Section 2.2.2. At the Month 12 reporting, all key secondary efficacy endpoints will be evaluated based on data from baseline to Month 12 (see Section 3.5). For the Month 12 analyses, post-baseline visits, up to and including Month 12, will be included and nominal p-values will be presented. At the time of the final study analysis, all key secondary efficacy endpoints will be evaluated based on data from baseline to Month 24, and formal statistical testing for key secondary endpoints will be performed as described in Section 6.3.1. Unless otherwise specified, all secondary efficacy endpoints will be analyzed for the mITT set.

### **6.3.1. Type I Error Management**

The planned submission of pegcetacoplan in GA consists of 2 studies of very similar design (APL2-303 and APL2-304), each with multiple endpoints. It is planned to control the type I error rate for the primary endpoint hypotheses testing at the level of the individual studies (as described in Section 6.2.1), and at a level of the submission as a whole for the key secondary endpoints hypotheses testing based on pooling APL2-303 and APL2-304. Figure 2 presents the overall hypotheses testing strategy for the APL2-303 and APL2-304 studies.

The primary endpoint hypotheses in the PM vs. Sham and PEOM vs. Sham will be tested in a hierarchical order within a study. If both hypothesis tests for the primary endpoint in both studies are statistically significant, then hypotheses testing will be performed for the key secondary endpoints within the pooled APL2-303/APL2-304 data for hypotheses  $H_{2a}$  –  $H_{4b}$  and within the APL2-304 study for  $H_{5a}$  and  $H_{5b}$  at the presented  $\alpha$  level. The key secondary efficacy endpoints hypotheses that will be tested in the pooled APL2-303/APL2-304 studies are below:

- $H_{2a}$  There is no difference between PM and Sham regarding mean change from baseline in monocular maximum reading speed (study eye), as assessed by MNRead or Radner Reading Charts at Month 24.
- $H_{2b}$ : There is no difference between PEOM and Sham regarding mean change from baseline in monocular maximum reading speed (study eye), as assessed by MNRead or Radner Reading Charts at Month 24.

- H3a: There is no difference between PM and Sham regarding mean change from baseline in mean FRI Index score at Month 24.
- H3b: There is no difference between PEOM and Sham regarding mean change from baseline in mean FRI Index score at Month 24.
- H4a: There is no difference between PM and Sham regarding mean change from baseline in NL-BCVA score at Month 24 (study eye) as assessed by ETDRS chart.
- H4b: There is no difference between PEOM and Sham regarding mean change from baseline in NL-BCVA score at Month 24 (study eye) as assessed by ETDRS chart.

The key secondary efficacy endpoints hypotheses that will be tested within the APL2-304 study are below:

[figure not shown]
- H5a: There is no difference between PM and Sham regarding mean change from baseline in mean threshold sensitivity of all points (study eye) for the evaluation of the macular functional response, as assessed by mesopic microperimetry at Month 24.
- H5b: There is no difference between PEOM and Sham regarding mean change from baseline in mean threshold sensitivity of all points (study eye) for the evaluation of the macular functional response, as assessed by mesopic microperimetry at Month 24.

Hypothesis tests will be conducted in the order indicated by the arrows in [Figure 2](#) and will continue as long as all preceding hypotheses are rejected at a given  $\alpha$  level. If both the PM vs. Sham and the PEOM vs. Sham comparisons are statistically significant for a given key secondary endpoint, then the  $\alpha$  will be allocated equally to the other key secondary hypotheses. At the study-level, the type I error rate (one-sided) is controlled at 0.025 for the primary endpoint hypotheses. In the submission, the type I error rate (one-sided) is controlled at 0.000625 (0.025) for the primary endpoint hypotheses and at 0.025 for the key secondary endpoint hypotheses. All hypothesis tests will be adjusted for the number of DMC unmasked reviews prior to the Month 12 analysis.

Type I error will be controlled by the testing procedure via the graphical methods approach ([Bretz 2009](#)). All confidence intervals and p-values will be presented without adjustments.

[figure not shown]
If at least one of the hypothesis tests for the primary endpoint in the APL2-303 study is not statistically significant but both hypothesis tests for the primary endpoint in the APL2-304 study are statistically significant, then any hypothesis testing for the key secondary endpoints will not be rejected at the submission level. Within the APL2-304 study hypotheses testing for the key secondary endpoints will be tested as shown in [Figure 3](#) and type I error will be controlled using a fixed sequencing approach. All hypotheses tests will be adjusted for the number of DMC unmasked reviews prior to the Month 12 analysis. All confidence intervals and p-values will be presented without adjustments.

**Figure 2: APL2-303 and APL2-304 Hypothesis Testing and Type I Error Control**

Endpoint data are compared to sham injections in hypotheses testing. Hypotheses can only be tested in sequential order as indicated by arrows. Sequential testing will continue as long as all preceding hypotheses can successfully be rejected at the given alpha level. At the study-level, the Type I error rate (one-sided) is controlled at 0.025 for the primary endpoint hypotheses. In the submission, the Type-I error rate (one-sided) is controlled at 0.000625 ( $0.025^2$ ) for the primary endpoint hypotheses and at 0.025 for the key secondary endpoints.

**Figure 3: APL2-304 Hypothesis Testing and Type I Error Control If There is No  $\alpha$  Remaining in APL2-303 to Allow Pooling Secondary Functional Endpoints**

Endpoint data are compared to sham injections in hypotheses testing. Hypotheses can only be tested in sequential order as indicated by arrows. Sequential testing will continue as long as all preceding hypotheses can successfully be rejected at the given alpha level. This testing tree will only be used when APL2-303 cannot pass  $\alpha$  from the primary endpoint testing to the pooled secondary functional endpoint testing.

## 6.3.2. Main Analyses of Key Secondary Efficacy Endpoints

### 6.3.2.1. Mean Threshold Sensitivity of All Points

Mean threshold sensitivity of all points will be determined from the mesopic microperimetry as an assessment of the macular functional response.

Mean threshold sensitivity of all points in the study eye will be summarized and analyzed in a similar fashion as the primary efficacy endpoint using MMRM described in Section 6.2.2. The model will include treatment (PM, PEOM, Sham), presence of CNV in the fellow eye (yes or no), and baseline GA lesion area ( $< 7.5 \text{ mm}^2$  or  $\geq 7.5 \text{ mm}^2$ ) as fixed effects; baseline mean threshold sensitivity of all points as a covariate, time (in months) as a factor; the time  $\times$  treatment interaction term as well as the mean threshold sensitivity of all points  $\times$  time interaction term.

The observed values for mean threshold sensitivity of all points will be summarized by treatment group and visit for both the study and the fellow eye. Summaries will present the descriptive statistics for baseline, absolute values and change from baseline data.

The mean change from baseline in the mean threshold sensitivity of all points of the study eye  $\pm$  the standard error as well as the LS mean of the change from baseline in the mean threshold sensitivity of all points of the study eye  $\pm$  the standard error will be plotted over time by treatment group.

Data that is not acceptable quality for the main analysis, as identified by the reading center per the Imaging Charter, will not be included in this analysis.

All microperimetry data will be listed for the ITT Set.

### 6.3.2.2. Monocular Maximum Reading Speed

Maximum reading speed will be calculated per MNRead or Radner user manuals, with no adjustment for reading inaccuracy. An additional step to cap resulting reading speed values at a maximum of 300 words per minute will be implemented. Values above 300 words per minute exceed values reported in the literature for adults with no vision impairment for MNRead (Calabrese et al. 2016) or Radner (Radner et al. 2002; Radner and Diendorfer 2014) assessments. Maximum reading speed will be calculated as the mean of the three highest nonzero reading speeds (or two, or one value, as available) (Baskaran et al. 2019; Patel et al. 2011), except when all words per minute are calculated as 0: then the maximum reading speed will be calculated as 0.

Monocular maximum reading speed in the study eye will be summarized and analyzed in a similar fashion as the primary efficacy endpoint using MMRM described in Section 6.2.2. The model will include treatment (PM, PEOM, Sham), presence of CNV in the fellow eye (yes or no), and baseline GA lesion area ( $< 7.5 \text{ mm}^2$  or  $\geq 7.5 \text{ mm}^2$ ) as fixed effects; baseline monocular maximum reading speed as well as the chart type (MNRead or Radner) as covariates, time (in months) as a factor; the time  $\times$  treatment interaction term as well as the baseline monocular maximum reading speed  $\times$  time interaction term.

The observed values for the monocular maximum reading speed will be summarized by treatment group and visit for both the study and the fellow eye. Summaries will present the descriptive statistics for baseline, absolute values and change from baseline data.

The mean change from baseline in the monocular maximum reading speed of the study eye  $\pm$  the standard error as well as the LS mean of the change from baseline in the monocular maximum reading speed of the study eye  $\pm$  the standard error will be plotted over time by treatment group.

In addition, the categorical changes (improvements of  $\geq 20$  to  $<40$ ,  $\geq 40$  to  $<60$ ,  $\geq 60$  and minimal/no change ( $-20$  to  $20$ ), worsening of  $\geq 20$  to  $<40$ ,  $\geq 40$  to  $<60$ ,  $\geq 60$ ) for the study eye will be summarized by treatment group and visit.

The shift from baseline in the monocular maximum reading speed for the study eye categories over time will be presented by treatment group for the following categories:

- $< 40$  wpm
- $40$  to  $< 80$  wpm
- $80$  to  $<160$  wpm
- $\geq 160$  wpm

All monocular maximum reading speed data will be listed for the ITT set.

